## 8.3 Ibrutinib dose modifications

CTCAE System/Organ/Class (SOC)	ADVERSE EVENT	AGENT	ACTION**
Investigations	Neutrophil count decreased Grade 4	Ibrutinib	If the AE does not return to $\leq$ Grade 2 after reduction of ixazomib to 2.3 mg, then reduce ibrutinib dose as per table 8.1. If no recovery on the 140 mg dose level, then discontinue study therapy and then proceed to survival follow-up.
Investigations	Platelet count decreased Grade 4		If the AE does not return to $\leq$ Grade 1 after reduction of ixazomib to 2.3 mg, then reduce ibrutinib dose as per table 8.1. If no recovery on the 140 mg dose level, then discontinue study therapy and then proceed to survival follow-up.

\*\* Use the following to describe actions in the Action column:

- **Omit** = The current dose(s) for the specified drug(s) during a cycle is skipped. The patient does not make up the omitted dose(s) at a later time.
- **Hold/Delay** = The current dose(s) of all drugs during a cycle is delayed. The patient does make up the delayed dose(s) when the patient meets the protocol criteria to restart drugs.
- **Discontinue** = The specified drug(s) are totally stopped.

Additional Adverse Events:

- The dose of ibrutinib will be omitted in case a patient experiences any of the following considered at least possibly related to ibrutinib:
  - Any Grade  $\geq 3$  or greater non-hematological toxicities (other than alopecia or fatigue) with the following considerations:
    - Grade 3 nausea, vomiting or diarrhea will be considered significant if they occur despite appropriate maximal anti-emetic and/or antidiarrheal therapy.
    - Grade 3 hyperglycemia will be a considered significant if the patient is symptomatic or glucose level is  $>300$  mg/ml despite appropriate administration of insulin and/or oral antidiabetic agents.
- Ibrutinib will be omitted until the non-hematologic AE recovers to Grade  $\leq 1$  or baseline and may be restarted at the original dose for the first occurrence.
- Upon each subsequent occurrence, ibrutinib is restarted at the next lower dose (as per Table 8.1) after recovery to Grade  $\leq 1$  or baseline.
- If Grade  $\geq 3$  non-hematological AE or Grade 4 neutropenia and thrombocytopenia occurs at the lowest dose, discontinue ibrutinib treatment. The treatment with ibrutinib should also be discontinued entirely if ibrutinib is omitted for 4 consecutive weeks or at the discretion of the Principal Investigator for patient safety. Patients may then continue with ixazomib monotherapy.
- Patient will discontinue ibrutinib and enter survival follow-up if AE is grade  $> 3$  bleeding (other than bruising) that is probably or definitely attributed to ibrutinib.
- Patients who require a dose reduction during a given cycle will remain at that dose for at least 2 additional cycles. **At the investigator discretion, the dose of ibrutinib may be re-escalated after 2 cycles of a dose reduction in the absence of a recurrence of the toxicity that led to this reduction.**

This is particularly reasonable based upon the long-term safety data now available in Ibrutinib treated patients that show that most of the hematological or non-hematological AEs either decreased or remained stable.

If multiple AEs are seen, administer the dose based on the greatest reduction required by any single AE observed. Dose modifications are for AEs attributed to study treatment only. Dose modifications are not required for AEs if they are deemed unlikely or unrelated to study treatment.

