## 8.0 Dosage Modification Based on Adverse Events

A dose of ixazomib and ibrutinib (as per attribution by the treating physician) is held if a patient experiences any of the following considered at least possibly related to ixazomib and/or ibrutinib at the beginning of a new cycle of treatment:

- ANC <1,000/mm^3 (grade 2)
- Platelet <75,000/mm^3 (grade 1)
- Any other nonhematologic toxicity (except for alopecia or fatigue)  $\geq$  grade 3 with the

following considerations:

- Grade 3 nausea, vomiting or diarrhea will be considered significant if they occur despite appropriate maximal anti-emetic and/or antidiarrheal therapy.
- Grade 3 hyperglycemia will be considered significant if the patient is symptomatic or glucose level is >300 mg/ml despite appropriate administration of insulin and/or oral antidiabetic agents.

→ **ALERT:** **ADR reporting may be required for some adverse events (See Section 10.0)** ←

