**8.1 Dose Levels (Based on Adverse Events in Tables 8.2 and 8.3)**

Dose Level	Ixazomib	Ibrutinib
Starting Dose	4.0 mg	420 mg
-1	3.0 mg	280 mg
-2	2.3 mg	140 mg
-3	Discontinue	Current dose

NOTE: If ixazomib is discontinued, the patient can continue on single-agent ibrutinib at the dose the patient is on when ixazomib is discontinued.

→ → Use the NCI Common Terminology Criteria for Adverse Events (CTCAE) current version 4.0\* unless otherwise specified ← ←

\* Located at [http://ctep.cancer.gov/protocolDevelopment/electronic\\_applications.ctc.htm](http://ctep.cancer.gov/protocolDevelopment/electronic_applications.ctc.htm)

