## 8.2 Ixazomib dose modifications

CTCAE System/Organ/Class (SOC)	ADVERSE EVENT	AGENT	ACTION**
Investigations	Neutrophil count decreased Grade 4		*Omit dose until AE has resolved to Grade 2 or better • Follow CBC weekly * If neutropenia has resolved to $\leq$ Grade 2, resume dose at one level lower *If, after ixazomib has been omitted, and the AE does not return to $\leq$ Grade 2 within 4 weeks, then the patient may continue on single-agent ibrutinib till the completion of treatment and then proceed to survival follow-up
Blood and lymphatic system disorders	Febrile neutropenia $\geq$ Grade 3	Ixazomib	• Omit dose and follow CBC weekly • If neutropenia has resolved to $\leq$ Grade 2, resume dose at same level with GCSF support (See Section 9.2)
Investigations	Platelet count decreased Grade 4		*Omit dose until AE has resolved to Grade 1 or better • Follow CBC weekly • If thrombocytopenia $<25,000/\text{mm}^3$ recurs, reduce dose by one dose level and continue therapy when platelet count $\geq 75,000/\text{mm}^3$ If, after ixazomib has been omitted, and the AE does not return to $\leq$ Grade 1 within 4 weeks, then the patient may continue on single-agent ibrutinib till the completion of treatment and then proceed to survival follow-up

CTCAE System/Organ/Class (SOC)	ADVERSE EVENT	AGENT	ACTION**
Nervous System Disorders	Peripheral Motor Neuropathy and Peripheral Sensory Neuropathy. Grade 2 or Grade 1 with pain		Omit ixazomib until resolution to Grade $\leq$ 1 without pain or baseline. *If, after ixazomib has been omitted, and the AE does not return to $\leq$ Grade 1 within 4 weeks, then the patient may continue on single-agent ibrutinib till the completion of treatment and then proceed to survival follow-up
	New or worsening Grade 2 peripheral motor neuropathy and peripheral sensory neuropathy with pain or Grade 3		Omit ixazomib until resolution to Grade $\leq$ 1 without pain or baseline and then reduce ixazomib to next lower dose upon recovery. *If, after ixazomib has been omitted, and the AE does not return to $\leq$ Grade 1 within 4 weeks, then the patient may continue on single-agent ibrutinib till the completion of treatment and then proceed to survival follow-up.
	New or worsening Grade 4 peripheral neuropathy		Discontinue ixazomib. The patient may continue on single-agent ibrutinib till the completion of treatment and then proceed to survival follow-up.

\*\* Use the following to describe actions in the Action column:

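### For unresolved grade 4 neutropenia or thrombocytopenia, Section 8 gives conflicting instructions in two situations: at ibrutinib 140 mg, and at ixazomib 2.3 mg

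*Combined protocol and SAP*

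**What the plan says.** Four places in Section 8 govern unresolved grade 4 counts.

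- **Table 8.1 and its note.** Ixazomib steps down from 4.0 to 3.0 to 2.3 mg, and ibrutinib from 420 to 280 to 140 mg. Row -3 stops ixazomib and leaves ibrutinib where it is. The note adds that "the patient can continue on single-agent ibrutinib at the dose the patient is on when ixazomib is discontinued".
- **Section 8.2, grade 4 neutrophil and platelet rows.** Ixazomib is omitted until the count recovers (grade 2 for neutrophils, grade 1 for platelets). If that has not happened within 4 weeks, the patient is permitted to stay on ibrutinib alone for the rest of treatment. No ibrutinib dose is stated there.
- **Section 8.3 table, the same two grade 4 rows.** The rule for a count that does not recover reads "after reduction of ixazomib to 2.3 mg, then reduce ibrutinib dose as per table 8.1". The next step is "If no recovery on the 140 mg dose level, then discontinue study therapy and then proceed to survival follow-up".
- **Section 8.3, additional bullets.** Grade 4 neutropenia and thrombocytopenia at the lowest dose leads to ibrutinib being stopped. The bullet ends: "Patients may then continue with ixazomib monotherapy".

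Section 8.0 adds a separate check on counts (ANC below 1,000, platelets below 75,000). It opens "A dose of ixazomib and ibrutinib (as per attribution by the treating physician) is held if a patient experiences any of the following" and is limited to events "at least possibly related to ixazomib and/or ibrutinib at the beginning of a new cycle of treatment".

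**The concern.** These are safety instructions for grade 4 events, and treatment starts at two centres (Section 6.5). If two sentences fit the same patient and point to different actions, two investigators can both follow the protocol and manage that patient differently.

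The choice also reaches the endpoint. On treatment, Section 4.1 schedules IgM, immunofixation and, to document CR, bone marrow. Survival follow-up under Section 4.2 schedules event monitoring only. A CR needs two consecutive evaluations with a second immunofixation (Section 16.311), so a patient moved off treatment has less scheduled opportunity to have one confirmed. The final rule turns on 3 against 4 successes in 37 patients (Section 16.212), so in principle one patient's route could matter.

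**Working it through.** No sample size, power or error rate is involved, so there is nothing to recompute. The check is to take one patient in each situation and see what each rule requires.

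**Situation 1: ibrutinib 140 mg, grade 4 cytopenia, no recovery**

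| | Section 8.3 table | Section 8.3 bullet |
|---|---|---|
| Trigger | No recovery at 140 mg, after ixazomib has reached 2.3 mg | Grade 4 neutropenia and thrombocytopenia occurring at the lowest dose |
| Ibrutinib | Stopped | Stopped |
| Ixazomib | Stopped, as part of study therapy | May continue alone |
| Next phase | Survival follow-up | Stays on treatment if ixazomib continues |

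Table 8.1 makes 140 mg the lowest ibrutinib dose, so both triggers refer to the same level. They differ in two respects: the table speaks of failure to recover and the bullet of occurrence, and the bullet joins the two cytopenias with *and*. A patient on ixazomib 2.3 mg and ibrutinib 140 mg who has both counts at grade 4, without recovery, meets both triggers on the strictest reading. If the *and* covers either cytopenia, one low count is enough. The instructions then differ on ixazomib and on the next phase.

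**Situation 2: ixazomib 2.3 mg, grade 4 cytopenia, no recovery within 4 weeks**

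| | Section 8.2 with Table 8.1 | Section 8.3 table |
|---|---|---|
| Trigger | No recovery within 4 weeks of omitting ixazomib | No recovery after ixazomib has been reduced to 2.3 mg |
| Ixazomib | Stopped | Not stated |
| Ibrutinib | May continue, at the current dose | Reduced one level |

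The permissive wording of Section 8.2 does not remove the difference. If ibrutinib continues, Table 8.1 keeps its dose and Section 8.3 lowers it. The immediate disagreement is over dose. Further non-recovery on the Section 8.3 route leads to the 140 mg step, and so to Situation 1.

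**Is there a tie-break?**

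- The greatest-reduction rule in Sections 8.2 and 8.3 applies when a patient has several adverse events. It does not choose between two rules for one event.
- Section 13.3 takes a patient off treatment after an omission of more than 28 days for ixazomib and ibrutinib. It does not settle the branches in which one drug continues.

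**Who can reach these situations?** From the starting doses, ixazomib 2.3 mg is two reductions down (4.0 to 3.0 to 2.3), or one if the trial has moved to the 3 mg start of Table 7.1b. Ibrutinib 140 mg is two reductions down (420 to 280 to 140). The documents give no cytopenia rate, so the expected number of patients cannot be calculated.

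**The case against.** The strongest reply is that the rules mostly cover different states. The Table 8.1 note applies once ixazomib is discontinued; the Section 8.3 table applies after ixazomib has been reduced to 2.3 mg. The 140 mg bullet can also be reached through non-hematologic reductions while ixazomib is at a higher level. The Section 8.3 trigger is hard to reach as written, because Section 8.2 requires recovery before ixazomib is resumed at a lower dose. All of this narrows the point, but it leaves the two overlaps above.

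Three stronger readings are tempting, and the documents do not support them.

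- *Every patient with unresolved grade 4 cytopenia faces conflicting rules.* This is not so. A patient on ixazomib 4 mg whose neutropenia is attributed to ixazomib and does not recover in 4 weeks falls under Section 8.2. The Section 8.3 table is not triggered, because ixazomib never reached 2.3 mg.
- *Section 8.0 orders ibrutinib held while Section 8.2 continues it.* Section 8.0 is limited to cycle start and follows the physician's attribution. If the low count is attributed to ixazomib alone, ibrutinib need not be held and the two sections agree. They overlap on day 1 without explanation, which is a reason to clarify rather than a demonstrated contradiction.
- *The grade labels make one grade both a hold and a restart.* Section 8.0 attaches grade 1 to platelets below 75,000 and grade 2 to ANC below 1,000. Read as the boundary below which drug is held, these fit Section 8.2, whose platelet row also uses 75,000. The label is loose, but the platelet counts agree.

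It is also fair to say that the route does not alter the primary denominator (Section 16.311) and that Section 13.3 asks for End of Treatment procedures when a patient stops early. That limits the loss of response data. It does not restore the on-treatment schedule.

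**Conclusion.** The conflict holds in two situations: at ibrutinib 140 mg without recovery, where one rule ends all study therapy and another allows ixazomib alone; and at ixazomib 2.3 mg without recovery within 4 weeks, where one rule keeps the ibrutinib dose and another reduces it. The first is the more serious, because it lies within a single section and separates continued treatment and assessment from event monitoring only.

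The size is unknown. Only patients who reach these dose levels and then have unresolved grade 4 counts are affected, and the effect on the CR count cannot be computed.

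The conclusion rests on two readings: that the lowest dose in the bullet means ibrutinib 140 mg, and that failure to recover after reduction to 2.3 mg includes a grade 4 episode arising on that dose. It implies no view on which instruction is clinically right.

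**What to change.** The sponsor should reconcile Table 8.1 with its note, the grade 4 rows of Section 8.2, and the table and bullets of Section 8.3 into one pathway for these two situations. For each, the text should state what happens to each drug and which study phase follows, and should say whether the bullet's trigger is either cytopenia or both.

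The same amendment should say how the Section 8.0 check "at the beginning of a new cycle of treatment" relates to Section 8.2 and tidy its grade labels. Section 13.3 should be checked for agreement with the result.

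Which rule applies is for the sponsor to decide. The cost is amendment wording in Section 8, with no effect on sample size or data collection.

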## 9.0 Ancillary Treatment/Supportive Care

### 9.1 Full supportive care

Patients should receive full supportive care while on this study. This includes blood product support, antibiotic treatment, and treatment of other newly diagnosed or concurrent medical conditions. All blood products and concomitant medications such as antidiarrheals, analgesics, and/or antiemetics received from the first day of study treatment administration until 30 days after the final dose will be recorded in the medical records.

### 9.2 Blood products and growth factors

Blood products and growth factors should be utilized as clinically warranted and following institutional policies and recommendations. The use of growth factors should follow published guidelines of the Journal of Clinical Oncology, Volume 33, No 28 (October 1), 2015: pp. 3199-3212 (WBC growth factors) AND Journal of Clinical Oncology, Volume 28, No 33 (November 20), 2010: pp. 4955-5010 (darbepoetin/epoetin).

### 9.3 Antiemetics

Antiemetics may be used at the discretion of the attending physician.

### 9.4 Diarrhea

Diarrhea could be managed conservatively with loperamide. The recommended dose of loperamide is 4 mg at first onset, followed by 2 mg every 2-4 hours until diarrhea free (maximum 16 mg/day).

In the event of Grade 3 or 4 diarrhea, the following supportive measures are allowed: hydration, octreotide, and antidiarrheals.

If diarrhea is severe (requiring intravenous rehydration) and/or associated with fever or severe neutropenia (Grade 3 or 4), broad-spectrum antibiotics must be prescribed.

Patients with severe diarrhea or any diarrhea associated with severe nausea or vomiting **should be hospitalized** for intravenous hydration and correction of electrolyte imbalances.

### 9.5 Prior or Concomitant treatment:

- Ancillary treatments will be given as medically indicated; they should be recorded in the patient's medical chart and on the appropriate Case Report Form (CRF).
- Radiotherapy may be given concomitantly for control of bone pain BUT NOT for lesions considered due to disease progression. If possible, not all evaluable lesions should be included in the irradiated field. If this cannot be realized, the patient will be removed from the study and will not be evaluable for response from that moment on. Any lesion within the irradiated area cannot be used as a parameter for response assessment. The area should therefore be as small as possible.
- Patients will not receive other anticancer treatments or other investigational agents from start of study treatment until last study treatment. (Hormonal therapy for prior history of prostate or breast cancer are allowed).
- Due to potential of increased risk of viral infections, patients must be treated with antiviral prophylaxis starting Day 1 of treatment (e.g., acyclovir, valacyclovir or other).
- **For Ibrutinib:** Avoid co-administration with strong or moderate CYP3A inhibitors and consider alternative agents with less CYP3A inhibition. Concomitant use of strong CYP3A inhibitors which would be taken chronically (e.g., ritonavir, indinavir,

nelfinavir, saquinavir, boceprevir, telaprevir, nefazodone) is not recommended. For short-term use (treatment for 7 days or less) of strong CYP3A inhibitors (e.g., antifungals and antibiotics) consider interrupting ibrutinib therapy until the CYP3A inhibitor is no longer needed. Reduce ibrutinib dose to 140 mg if a moderate CYP3A inhibitor must be used (e.g., fluconazole, darunavir, erythromycin, diltiazem, atazanavir, aprepitant, amprenavir, fosamprenavir, crizotinib, imatinib, verapamil, and ciprofloxacin). Patients taking concomitant strong or moderate CYP3A inhibitors should be monitored more closely for signs of ibrutinib toxicity. Any strong CYP3A inducers should be avoided concomitantly with ibrutinib (<http://medicine.iupui.edu/clinpharm/ddis/main-table/>). Avoid grapefruit and Seville oranges during ibrutinib treatment, as these contain moderate inhibitors of CYP3A. No dose adjustment is required in combination with mild inhibitors.

- **For Ixazomib:** Systemic treatment with any of the following metabolizing enzyme inducers should be avoided, unless there is no appropriate alternative medication for the patient's use: Strong CYP3A inducers (rifampin, rifapentine, rifabutin, carbamazepine, phenytoin, phenobarbital, and St. John's Wort).
- **Antiplatelet agents and anticoagulants:** Warfarin or vitamin K antagonist administration should be avoided concomitantly with ibrutinib. Supplements such as fish oil and vitamin E preparations should be avoided. Use ibrutinib with caution in subjects requiring other anticoagulants or medications that inhibit platelet function. Subjects requiring the initiation of therapeutic anticoagulation therapy (e.g., atrial fibrillation), consider the risks and benefits of continuing ibrutinib treatment. If therapeutic anticoagulation is clinically indicated, treatment with ibrutinib should be held and not be restarted until the subject is clinically stable and has no signs of bleeding. Subjects should be observed closely for signs and symptoms of bleeding. No dose reduction is required when study drug is restarted.

## 10.0 Adverse Event (AE) Monitoring and Reporting

The site principal investigator is responsible for reporting any/all serious adverse events to the sponsor as described within the protocol, regardless of attribution to study agent or treatment procedure.

The sponsor/sponsor-investigator is responsible for notifying FDA and all participating investigators in a written safety report of any of the following:

- Any suspected adverse reaction that is both serious and unexpected.
- Any findings from laboratory animal or *in vitro* testing that suggest a significant risk for human subjects, including reports of mutagenicity, teratogenicity, or carcinogenicity.
- Any findings from epidemiological studies, pooled analysis of multiple studies, or clinical studies, whether or not conducted under an IND and whether or not conducted by the sponsor, that suggest a significant risk in humans exposed to the drug
- Any clinically important increase in the rate of a serious suspected adverse reaction over the rate stated in the protocol or Investigator's Brochure (IB).

Summary of SAE Reporting for this study  
(please read entire section for specific instructions):

WHO:	WHAT form:	WHERE to send:
All sites	
Pregnancy Reporting  http://ctep.cancer.gov/protocolDevelopment/electronic_applications/docs/PregnancyReportFormUpdated.pdf
	
Mayo Sites – attach to MCCC Electronic SAE Reporting Form  http://livecycle2.mayo.edu/workspace/?startEndpoint=MC4158-56/Processes/MC4158-56-Process.MC4158-56            Will automatically be sent to [contact] and [contact]            Non Mayo sites – complete and forward to [contact]

Mayo Clinic Sites	
Mayo Clinic Cancer Center SAE Reporting Form:http://livecycle2.mayo.edu/workspace/?startEndpoint=MC4158-56/Processes/MC4158-56-Process.MC4158-56            AND attach            MedWatch 3500A:  http://www.fda.gov/downloads/AboutFDA/ReportsManualsForms/Forms/UCM048334.pdf
	
Will automatically be sent to [contact] and [contact]

### Definitions

#### *Adverse Event*

Any untoward medical occurrence associated with the use of a drug in humans, whether or not considered drug related.

#### *Suspected Adverse Reaction*

Any adverse event for which there is a reasonable possibility that the drug caused the adverse event.

#### *Expedited Reporting*

Events reported to sponsor within 24 hours, 5 days or 10 days of study team becoming aware of the event.

#### *Routine Reporting*

Events reported to sponsor via case report forms

#### *Events of Interest*

Events that would not typically be considered to meet the criteria for expedited reporting, but that for a specific protocol are being reported via expedited means in order to facilitate the review of safety data (may be requested by the FDA or the sponsor).

